## Statistical Analysis Plan

(a) ignoring gender (b) split by gender and (c) incorporating gender as a factor. This analysis will be repeated at T3. Partial eta squared as a measure of effect size will be reported.

Underpinning model assumptions will be examined. In the ANCOVA post hoc analyses, the homogeneity of regression lines assumption will be assessed and appropriate simplification will be undertaken if the parallel lines assumption is justifiable. Percentages reporting positive change, no change, and a poorer outcome, along with 95% confidence intervals will be reported

**Table 6.1** Descriptive statistics for BESAA using ITT data set. *N* = sample size, *LQ* = Lower Quartile, *Md* = Median, *M* = Mean, *UQ* = Upper Quartile, *SD* = Standard Deviation

Measure	Group	N	LQ	Md	M	UQ	SD
BESAA (T1)	Comic Control						
BESAA (T2)	Comic Control						
BESAA (T3)	Comic Control						
DELTA BESAA (T2 – T1 )	Comic Control						
DELTA BESAA (T3 – T1)	Comic Control						
DELTA BESAA (T3 – T2)	Comic Control						

**Table 6.2** Descriptive statistics for baseline covariate adjusted BES using ITT data set. *N* = sample size, *LQ* = Lower Quartile, *Md* = Median, *M* = Mean, *UQ* = Upper Quartile, *SD* = Standard Deviation

Measure	Group	N	LQ	Md	M	UQ	SD
BES (T2)	Comic Control						
BES (T3)	Comic Control						

## Statistical Analysis Plan

---

### 6.1 Secondary Outcome measures

All secondary outcome measures will be analysed as per the data analysis plan for BESSA.

### 6.2 Exploratory Outcomes

The exploratory outcome “Endorsement of traditional gender roles” is scale data and will be analysed as per the analysis plan for the primary and secondary outcomes.

The exploratory measures (i) Skin colour dissatisfaction (ii) Body hair dissatisfaction and (iii) Appearance-based teasing are each on a five-point ordinal scale. These outcomes will be assessed at T2 using ordinal logistic regression providing the parallel lines assumption is not grossly violated to the extent of conclusions being questionable. In these latter events an ordinal series of binary logistic models will be used to better understand the outcomes. The logistic models will comprise (i) baseline covariate (ii) randomised arm (iii) gender. Separate analyses will also be conducted for each gender too. Analysis at T3 will mirror the analysis at T2.

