## 1. Trial Summary

The trial is a substantial pragmatic parallel two arm prospective clustered randomised controlled trial to evaluate efficacy of a novel school-based Hindi comic body image intervention in a rural India setting. Schools will be randomised to control or intervention (randomisation with minimisation with target 1:1 with error component). The trial design and its rationale are fully documented in the trial protocol document and in the published study protocol manuscript (Lewis-Smith, H., Hasan, F., Ahuja, L., White, P., & Diedrichs, P. (2022). A comic-based body image intervention for adolescents in semi-rural Indian schools: Study protocol for a randomized controlled trial. *Body Image*).

This document is concerned with the data analysis of the accruing data for the study. The statistical analysis of the study is performed in accordance with the principles stated in the CONSORT guideline statement, with due regard to the SPIRIT guidelines (see Annex 1), and in keeping with Consensus Guideline E9 (Statistical Principles for Clinical Trials) of the International Conference on Harmonisation (ICH).

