### 3 Randomisation

Participants will be randomized to either the intervention or control arm at the school level. Randomization will be conducted at the school level to avoid potential spill over effects within a school. Eligible schools will be randomised in a target 1:1 ratio using minimisation with a residual error. The minimisation factors are (i) number of students at grade 6, 7 or 8 and (ii) proportion of boys at grade 6, 7, and 8. The first 8 schools will be allocated using blocked randomisation thereafter probabilistic minimisation will occur with the probability of minimising set to 0.8. Randomisation will be done in the UK.

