### 6.1 Primary outcome

The primary outcome of body image will be measured using the Body Esteem Scale for Adults and Adolescents. The BESAA is comprised of three subscales (*Appearance, Weight and Attribution*) and asks participants about their thoughts and feelings in relation to their body and appearance. Responses to items will be indicated using a 5-point Likert scale, ranging from 1 (*Never*) to 5 (*Always*), with higher scores indicating greater dissatisfaction. Only the combined mean scores for the Appearance and Weight subscales will be used in analyses, as the Attribution subscale relates to the perception of others' attitudes towards one's appearance. The English language BESAA has demonstrated good internal and re-test reliability and construct validity among Indian adolescents and other globally diverse adolescent samples. A Hindi version of the scale will be used in this study.

Table 4.1 summarises the descriptive statistics that will be extracted for BESSA. These data will be further summarised graphically using box-and-whisker plots, error bar graphics, scatterplots and similar as appropriate. Effect size will be calculated using Cohen's *d* and 95% confidence intervals for Cohen's *d* will also be given. Percentages reporting positive change, no change, and a poorer outcome, along with 95% confidence intervals will be reported.

The primary analysis will be a linear mixed model with random intercepts with school declared as a random factor. The model will additionally include the three main effects, three two-way interactions, and the three-way interaction for randomised arm (between subjects fixed effect factor with 2 levels comic intervention and control), study phase (repeated measures fixed effect factor with two levels T2 and T3), gender (between subjects fixed effects factor with 2 levels, male and female) and include a baseline measure as a covariate, and the three two-way interactions between covariate and each of randomised arm, gender, and phase). An overall assessment of the contribution of randomised arm to the model will be undertaken using the change in the log-likelihood statistic between its inclusion and exclusion from the model. Post hoc analyses will proceed primarily comparing the two randomised arms at T2 controlling for baseline covariate

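### The logistic models for three exploratory outcomes leave out school, although schools are randomised, so p-values for arm are too small if pupils within a school remain correlated

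*SAP*

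**What the plan says.** Section 1 calls the study a "parallel two arm prospective clustered randomised controlled trial". Section 3 fixes the unit of allocation: "Participants will be randomized to either the intervention or control arm at the school level".

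For body esteem, section 6.1 (Primary outcome) provides for this: "The primary analysis will be a linear mixed model with random intercepts with school declared as a random factor". The secondary outcomes follow the same plan.

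Section 6.2 divides the exploratory outcomes. The gender-roles scale "is scale data and will be analysed as per the analysis plan for the primary and secondary outcomes", so it inherits the school effect. The three single-item outcomes get a different method: ordinal logistic regression, with a series of binary logistic models if the parallel lines assumption fails badly. For these, "The logistic models will comprise (i) baseline covariate (ii) randomised arm (iii) gender". The section then extends the approach: "Separate analyses will also be conducted for each gender too. Analysis at T3 will mirror the analysis at T2".

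**The concern.** Arm varies only between schools. A model that treats pupils as independent credits the arm comparison with more information than the design gives. If pupils in a school still resemble each other after adjustment for baseline and gender, the model-based standard error for arm is too small, confidence intervals are too narrow and the false-positive rate exceeds 5%.

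The specification covers three outcomes at two time points, pooled and in each gender: 3 × 2 × 3 = 18 arm comparisons, before any fallback binary splits. Section 6 sets a two-sided 0.05 level for tests in general, and the false discovery rate control in 6.5 names only the secondary outcomes. No other stated safeguard applies to these p-values.

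**Working it through.** **Can school be read in from elsewhere?** Section 5 also says that school enters the model as a random factor, but the model described there is the factorial ANCOVA or linear mixed model. The school term in 6.1 belongs to the linear mixed model for body esteem. Section 6 and 6.1 (Secondary Outcome measures) extend that plan to the secondary outcomes, and 6.2 extends it to the gender-roles scale. None of these reaches the logistic models.

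**Inputs.** The SAP gives no figure of its own to reproduce on this point.
- From section 5: 2,400 recruited and 10% loss, so 2,400 × 0.9 = 2,160 analysed, or 1,080 per gender.
- From section 6: two-sided α = 0.05.
- Assumed, because not stated: J = 20, 40 or 100 equal-sized schools; residual ICC (after baseline and gender) of 0.005 to 0.05.

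**Formula check.** With m pupils per school, the design effect is DE = 1 + (m − 1) × ICC. The standard error is understated by a factor of about √DE, and the actual type I error is about 2 × [1 − Φ(1.96/√DE)].

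Example: J = 20, so m = 2,160/20 = 108. At ICC 0.01, DE = 1 + 107 × 0.01 = 2.07 and √DE = 1.44. Then 1.96/1.44 = 1.36, and the type I error is 0.173.

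| Pooled, by formula | ICC 0.005 | 0.01 | 0.02 | 0.05 |
|---|---|---|---|---|
| 20 schools (m = 108) | 0.114 | 0.173 | 0.269 | 0.437 |
| 40 schools (m = 54) | 0.081 | 0.113 | 0.172 | 0.305 |
| 100 schools (m = 21.6) | 0.062 | 0.074 | 0.099 | 0.169 |

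The factor √DE runs from √(1 + 20.6 × 0.005) = 1.05 (100 schools, ICC 0.005) to √(1 + 107 × 0.05) = 2.52 (20 schools, ICC 0.05).

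**Simulation of the ordinal model as listed.** Proportional-odds fit with baseline (five-level score), arm and gender, and a Wald test of arm. Half the schools were in each arm, with no true effect. The school effect was normal with variance ICC × (π²/3)/(1 − ICC) on the logit scale. There were 2,000 replicates per cell (Monte Carlo standard error at most 0.011) and 2,160 pupils (2,100 at 100 schools).

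| Simulated type I error | ICC 0 | 0.005 | 0.01 | 0.02 | 0.05 |
|---|---|---|---|---|---|
| Pooled, 20 schools | 0.053 | 0.114 | 0.176 | 0.288 | 0.440 |
| Pooled, 40 schools | 0.041 | 0.090 | 0.109 | 0.162 | 0.315 |
| Pooled, 100 schools | 0.052 | 0.060 | 0.074 | 0.095 | 0.151 |
| One gender, 20 schools | 0.044 | 0.092 | 0.120 | 0.182 | 0.310 |
| One gender, 40 schools | 0.042 | 0.064 | 0.071 | 0.118 | 0.208 |
| One gender, 100 schools | 0.057 | 0.057 | 0.056 | 0.068 | 0.099 |

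The formula and the simulation agree closely.

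**Simulation of the fallback binary model.** Split near the median, 1,000 replicates, ICC 0.01 / 0.02 / 0.05: 0.147 / 0.221 / 0.357 with 20 schools and 0.097 / 0.148 / 0.231 with 40. The error is inflated, but less than in the ordinal model.

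**Does the remedy work?** In the same binary runs, cluster-robust variance with a t reference on J − 2 degrees of freedom gave 0.047 to 0.060 in every scenario. A further check covering both ordinal and binary models gave 0.045 to 0.06.

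**The case against.** - **The list may name fixed terms only.** Section 6.1 declares school separately from its fixed effects, and section 5 shows that the authors recognise clustering. But where the SAP wants school in a model it says so, and 6.2 does not. An analyst following 6.2 literally would fit an ordinary logistic regression.
- **The ordinal table does not carry over to the binary models.** This stands. A given ICC on the logit scale means weaker correlation once the outcome is dichotomised. For a rare-category split (intercept −2.6, assumed baseline slope 0.5, 1,500 replicates), type I error at ICC 0.005 / 0.01 / 0.02 / 0.05 was 0.06 / 0.08 / 0.11 / 0.21 with 20 schools and 0.06 / 0.07 / 0.08 / 0.13 with 40. With 100 schools it stayed at 0.05 to 0.08. The inflation is smaller, and near nil in the mildest cells.
- **√DE is an approximation.** It assumes equal school sizes and a residual ICC. Baseline may absorb part of the school variation, and minimisation on grade size and proportion of boys may balance some of it. Both would reduce the inflation, but neither guarantees a residual ICC of zero.
- **These are exploratory single items.** This stands and limits the consequence: no primary or secondary conclusion rests on them. It does not make the standard errors right.

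**Conclusion.** The concern holds. This is wrong as written, not a detail left open: 6.2 states the model terms, and for a school-randomised trial those terms give an invalid standard error for arm whenever residual school correlation is positive.

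The size cannot be fixed from the SAP. Under the assumed ranges, the pooled ordinal type I error runs from 0.06 (100 schools, ICC 0.005) to 0.44 (20 schools, ICC 0.05), against a nominal 0.05. At ICC 0 there is no inflation. Single-gender and binary versions are affected less.

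The point should be corrected before analysis, but it is confined to three exploratory outcomes.

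**What to change.** In 6.2, add that the ordinal and binary logistic models include a school random intercept, or else use GEE or cluster-robust variance by school, with a named small-sample correction (for example a t reference on the number of schools minus 2). State that this applies equally to the by-gender and T3 versions.

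As a clarification only, 6.1 could say that the T2 and T3 post hoc ANCOVAs keep the school random effect declared for the primary model.

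The cost is a sentence and some programming, with no new data. Intervals for these three outcomes will be wider. A random-intercept model may converge poorly in sparse binary splits, so the SAP should name the GEE or cluster-robust analysis as the fallback.

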#### 4.2 Secondary Endpoints:

The data analysis plan for the primary outcome measure will be the same plan for all secondary outcome measures.

- (a) To assess changes in all outcome measures and their subscales over the study duration (between T1, T2, and T3) within each randomised arm.
- (b) To assess whether outcomes measures at T2 differ between randomised arms after controlling for commensurate baseline scores
- (c) To assess whether outcomes measures at T3 differ between randomised arms after controlling for commensurate baseline scores
- (d) To assess whether outcome measures change between T2 and T3 and whether any changes are dependent on randomised arm after controlling for commensurate baseline scores
- (e) To assess whether any differences in measures at T2 between randomised arms are gender specific after controlling for commensurate baseline scores
- (f) To assess whether any differences in measures at T3 between randomised arms are gender specific after controlling for commensurate baseline scores
- (g) To assess whether interventional changes in Body Esteem between T1 and T3, and Body Esteem at T3, are mediated by changes in internalisation of appearance ideals between T1 and T2, and whether mediation is gender dependent.

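### For the three ordinal exploratory items, Section 6.2 plans separate boys' and girls' models but no arm-by-gender term, so no formal test of a gender difference in the arm effect is specified

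*SAP*

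**What the plan says.** SAP Section 6.2 assigns three single five-point items to ordinal logistic regression, with a series of binary logistic models as fallback if the parallel lines assumption is grossly violated. It lists the terms and the gender split together: "The logistic models will comprise (i) baseline covariate (ii) randomised arm (iii) gender. Separate analyses will also be conducted for each gender too". For the later time point it adds "Analysis at T3 will mirror the analysis at T2". No product of arm and gender is listed, and no rule is given for comparing the boys' and girls' results.

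The scale outcomes are handled differently. Section 6.1 (Primary outcome) states "The model will additionally include the three main effects, three two-way interactions, and the three-way interaction for randomised arm", with study phase and gender as the other two factors, and it declares school a random factor. The secondary outcomes follow that plan. So does the fourth exploratory outcome, endorsement of traditional gender roles, under Section 6.2.

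Section 4.2(e) sets the question "To assess whether any differences in measures at T2 between randomised arms are gender specific after controlling for commensurate baseline scores", and 4.2(f) repeats it for T3. Section 6.3 names gender as the only planned subgroup. Section 6 says that effect sizes will be reported with the tests.

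**The concern.** A pooled model with main effects only assumes one arm odds ratio common to boys and girls, so it cannot show whether the effect differs by gender. Separate models give two estimates and two tests against no effect, but no test of one estimate against the other. A significant result in one gender and a non-significant one in the other is not evidence that the effects differ.

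Exploratory status does not explain the gap, because the fourth exploratory outcome receives the interaction. Only the three ordinal items go without it. What is at stake is that an effect shared by both genders could be described as specific to one of them.

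**Working it through.** **Model terms side by side**

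| | Scale outcomes (6.1 Primary outcome) | Three ordinal items (6.2) |
|---|---|---|
| Baseline, arm, gender | yes | yes |
| Arm-by-gender | yes | not listed |
| School | random factor | not listed |
| Split by gender | yes | yes |

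**Inputs from the SAP.** Section 5 gives d = 0.2, 540 per gender per arm before loss, two-sided alpha 0.05 and 95% power separately for each gender. This is the only power statement for separate gender analyses. It concerns a standardised mean effect, not a five-point item.

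**The plan's own figure.**
- Required n = 2(1.960 + 1.645)²/0.2² = 650 per gender per arm, not 540.
- At 540, power = Φ(0.2/√(2/540) − 1.960) = Φ(3.286 − 1.960) = 0.908.
- A one-sided 0.05 calculation gives 542, close to the stated figure.

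Both 95% (stated) and 90.8% (reproduced) are carried forward.

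**Chance that exactly one gender is significant when the true effects are equal.** With independent boys' and girls' estimates, each with power p, this is 2p(1 − p):
- p = 0.95: 2 × 0.95 × 0.05 = 9.5%
- p = 0.908: 2 × 0.908 × 0.092 = 16.7%, or 16.8% with unrounded power
- p = 0.80: 2 × 0.80 × 0.20 = 32%
- p = 0.50: 2 × 0.50 × 0.50 = 50%, the maximum
- No effect in either gender (p = 0.05): 9.5%

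Setting 2p(1 − p) = 0.05 gives an upper root of p = (1 + √0.9)/2 = 0.974. The rate therefore exceeds 5% for any power from 5% up to 97.4%. Simulation with one million pairs of independent estimates gave 9.5%, 16.8%, 31.9% and 50.0% for the first four rows. An interaction test on the same pairs rejected in 5.0%.

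**Sensitivity. The first line varies d; the design effects, category splits and odds ratios after it are assumptions, not SAP figures.**
- Other effects at 540 per gender per arm: d = 0.3 gives 0.3%, d = 0.15 gives 42.5% and d = 0.1 gives 46.9%.
- Design effects of 1.5, 2 and 3 at d = 0.2: power 0.765, 0.642 and 0.475; discordance 35.9%, 46.0% and 49.9%.
- Whitehead's ordinal approximation, no clustering: log odds ratio = 0.2π/√3 = 0.363 (odds ratio 1.44), information = (1080/12)(1 − Σπ³) with π the category proportions. From an even split over five categories to 70% in one category, power runs from 0.92 to 0.79 and discordance from 14.5% to 32.7%. At odds ratio 1.20 (d = 0.1), discordance is 41% to 48%.

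**Number of comparisons.** Three items at two time points make six boy/girl pairs. If all had an equal effect at 90.8% power, the expected number of discordant pairs is 6 × 0.168 = 1.0, against 6 × 0.05 = 0.3 false rejections from interaction tests.

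**The case against.** A reader might infer that the SAP will judge gender differences by setting the two separate models against each other, and that this will often mislead. The document supports neither step. It states no such decision rule, and the separate models can be read as descriptive. How often such a reading would err depends on per-item power, which the SAP does not give. The rate is 9.5% at its stated power and close to zero at d = 0.3; rates of 46% to 50% require smaller effects or assumed clustering.

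Nor is there a clear contradiction with Section 4.2(e) and (f). They stand under the secondary endpoints and refer only to measures, whereas 4.2(a) refers to all outcome measures. Whether they extend to the exploratory items is left open. It would also be wrong to say that the reader will see only two p-values, because Section 6 calls for effect sizes.

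Two technical points stand as well. Where boys and girls share schools, their estimates may be positively correlated, which lowers discordance below 2p(1 − p). And 5% is a fair comparator only if the interaction test accounts for school, which the Section 6.2 list does not mention.

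These points limit the size of the problem. They do not supply the missing test: the separate gender models show that gender is a planned question for these items, and Section 6.2 gives no formal way to answer it.

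**Conclusion.** The gap is real and small. For three exploratory items at T2 and T3, no formal test of a gender difference in the arm effect is specified, in contrast to every scale outcome, and nothing bars reading one significant and one non-significant gender model as a gender-specific effect. Under equal true effects and independent estimates, that reading would err in 9.5% of cases at the stated 95% power, in about 17% at the power that the SAP's inputs give, and in up to 50% at lower assumed power. The comparator is a nominal 5%, provided that clustering is handled. These rates carry over a power figure for a mean difference to ordinal items, so they indicate scale only. The primary and secondary conclusions are unaffected.

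**What to change.** In Section 6.2, add the arm-by-gender term to the ordinal models and to the fallback binary models, at T2 and T3, with school accounted for as in Section 6.1 (Primary outcome). Report the interaction with a 95% confidence interval and base any gender-specific statement on it. Present the per-gender odds ratios with confidence intervals as descriptive. State whether Section 4.2(e) and (f) cover the exploratory items.

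The cost is one interaction term, the handling of school, and a few sentences; no further data are needed. The downside is low power for the interaction. On the standardised scale, with 540 per gender per arm and no clustering, a between-gender difference of 0.2 is detected with power Φ(0.2/√(4/540) − 1.960) = 0.64, and clustering could reduce this further. Fewer gender claims will be made, and a non-significant interaction should not be reported as evidence of equal effects.

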### 6.3 Planned Sub-Group analyses

There are no planned sub-group analyses other than the gender subgroups as indicated in the main analysis.

### 6.4 Planned Subset analyses

There are no planned subset analyses.

### 6.5 Control of Error Rate

This study has multiple outcome measures (MOMs) at multiple time points. To limit serendipitous conclusions from MOMs, we will additionally report unadjusted  $p$ -values of the secondary outcomes at each of T2 and T3 along with results after controlling the False Discovery Rate (Benjamini & Hochberg, FDR using 0.2).

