### 1.2 Participant Measures

Measures are given in Hindi.

The primary outcome measure is the Body Esteem Scale for Adults and Adolescents (BESAA).

The secondary measures are (i) The Positive and Negative Affect Scale (PANAS) (ii) Rosenberg Self Esteem Scale (RSES) (iii) Life disengagement relating to body dissatisfaction using the Body Image Life Disengagement Questionnaire (BILD-Q) (iv) media internalisation using the Internalisation-General subscale from the Socio-Cultural Attitudes To Appearance Questionnaire Scale (SATAQ-3) and (v) disordered eating using the Eating Disorder Evaluation Questionnaire (EDE-Q).

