## Statistical Analysis Plan

---

sensitivity analysis will be undertaken to better understand the data. As appropriate, missing data sensitivity analyses will be performed on both the ITT **analysis** set and the PP **analysis** set.

In general, all statistical tests will be performed as two-sided tests with a nominal significance level of  $\alpha = 0.05$  and effect sizes reported.

There is no planned interim analysis for trial progression but there will regular reports to the trial steering committee and trial management group for oversight.

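### Does Benjamini-Hochberg control at 0.2 for the secondary outcomes undercut the SAP's nominal 0.05 level?

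*SAP*

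**What the plan says.** Section 6.5 addresses multiple outcomes at multiple time points. Its aim is "To limit serendipitous conclusions from MOMs", and its means is to report unadjusted p-values for the secondary outcomes at T2 and at T3 "along with results after controlling the False Discovery Rate (Benjamini & Hochberg, FDR using 0.2").

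Section 6 fixes the test level for the whole plan: "In general, all statistical tests will be performed as two-sided tests with a nominal significance level of" 0.05, with effect sizes reported.

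Section 1.2 lists five secondary measures, beginning "The secondary measures are (i) The Positive and Negative Affect Scale (PANAS) (ii) Rosenberg Self Esteem Scale (RSES"). Section 4.2 asks for an arm comparison on each at T2 (item b) and at T3 (item c). Section 6.1 asks for each comparison ignoring gender, split by gender, and with gender as a factor, and the secondary outcomes follow the same plan. Section 6.3 confirms gender as the only subgroup: "There are no planned sub-group analyses other than the gender subgroups as indicated in the main analysis".

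The SAP does not say which of these tests form the family for BH. Nor does it say how the unadjusted and the BH results combine when an outcome is described as different between arms.

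**The concern.** A step introduced to limit chance findings ought not to let through outcomes that the plan's own 0.05 would reject, yet at 0.2 it can. The comic is meant to act on several related outcomes, and several rejections are what push the BH cut-off above 0.05. A reader could take survival of FDR control as stronger evidence than p ≤ 0.05 when it may be weaker. With no stated claim rule, either list could be favoured once results are known. At stake are the statements made about secondary outcomes; the primary endpoint is outside this procedure.

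**Working it through.** **Inputs.** BH at q = 0.2 (Section 6.5); nominal two-sided 0.05 (Section 6); five secondary measures (Section 1.2) at two time points (Section 4.2 b and c). Family size m is an assumption: 5 for one time point, 5 × 2 = 10 for both, 5 × 2 × 2 = 20 if each gender is tested at both. The number of true effects and the power are also assumptions.

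**Cut-offs.** BH rejects the k smallest p-values, where k is the largest rank i with p(i) ≤ 0.2i/m. The cut-off 0.2k/m exceeds 0.05 when k > m/4.

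- m = 5: 0.04, 0.08, 0.12, 0.16, 0.20; above 0.05 from the second rejection.
- m = 10: 0.02, 0.04, 0.06, …; above 0.05 from the third.
- m = 20: exactly 0.05 at the fifth; above it from the sixth.

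**Example, m = 5.** p = 0.001, 0.07, 0.4, 0.6, 0.8. Rank 2: 0.07 ≤ 0.08, so it passes. Ranks 3 to 5 fail (0.4 > 0.12, 0.6 > 0.16, 0.8 > 0.20). Two outcomes are listed, one with p = 0.07. Its BH-adjusted p-value is 0.07 × 5/2 = 0.175.

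**What Section 6.5 promises.** For independent tests the FDR of BH is q × (number of nulls)/m. With two true of five this is 0.2 × 3/5 = 0.12; with two true of twenty, 0.2 × 18/20 = 0.18. It never exceeds 0.2.

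**Direction against unadjusted 0.05.** Simulation with independent tests and 90% power per true effect (non-null z mean 1.96 + 1.28 = 3.24), using 400,000 replicates (200,000 for m = 20). The unadjusted column agrees with 1 − 0.95^(number of nulls), for example 1 − 0.95³ = 0.143 for two true of five. The per-null rate is the chance that a given null outcome is listed; unadjusted it is 5.0% throughout.

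| m (true effects) | Any false positive, unadjusted 0.05 | Any false positive, BH 0.2 | Per-null rate, BH 0.2 | FDR, BH 0.2 |
|---|---|---|---|---|
| 5 (0) | 22.6% | 20.0% | 5.6% | 20.0% |
| 5 (1) | 18.5% | 28.3% | 9.3% | 16.0% |
| 5 (2) | 14.2% | 31.4% | 13.0% | 12.0% |
| 5 (4) | 5.0% | 19.5% | 19.5% | 4.0% |
| 10 (2) | 33.8% | 38.0% | 7.0% | 16.0% |
| 20 (2) | 60.3% | 40.0% | 3.5% | 18.0% |
| 20 (4) | 56.0% | 53.3% | 5.6% | 16.0% |

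With none true of ten, any false positive is 20% under BH against 40% unadjusted. For two true of five, the per-null rate is 8.5% at 30% power, 11.2% at 60% and 13.2% at 95%, and 13.4% with correlation 0.5 at 90% power. In that 90%-power independent case, 20% of trials list at least one null outcome with p > 0.05.

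**What a dual rule (BH at 0.2 and p ≤ 0.05) would buy, m = 5.**

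- Two true, 90% power: any false positive 14.2%, the same as unadjusted. Power 89.9%, against 93.7% for BH alone and 90.0% unadjusted.
- Two true, 60% power: power 59.1%, against 67.0% for BH alone.
- None true: any false positive 19.1%, against 20.0% for BH alone and 22.6% unadjusted.

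**The case for a change.** The strongest case for a change is that the SAP is where error control is settled, that Section 6.5 names neither a family nor a claim rule, and that two sentences would close the gap before results are seen. The excess is not confined to one convenient setting: correlation, lower power or pooling the time points into ten (7.0% per null with two true) shrinks it or leaves it, but does not remove it.

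The arithmetic of this stands, and so does the observation that the section is silent on how the two results combine. What does not follow is that the plan is wrong. The per-null rate is not the quantity that an FDR procedure controls or that Section 6.5 undertakes to control, and a q above the per-test level is a legitimate choice for secondary outcomes. The silence is also partial. Section 6 gives 0.05 as the general level, and Section 6.5 presents its results as additional reporting, so the natural reading keeps 0.05 as the test level with BH beside it. On that reading p = 0.07 is already non-significant.

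**Conclusion.** No change is needed. There are two ways to read Section 6.5. If 0.05 remains the test level, a sentence requiring p ≤ 0.05 as well as BH would only write down what Section 6 already says. If BH at 0.2 governs, adding a 0.05 filter is a trade-off rather than a correction: at 60% power with two true of five it costs about 8 percentage points of power (67.0% − 59.1% = 7.9), and where several effects are true it gives almost the error rate of uncorrected testing.

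The contrast of 13.0% with 5.0% holds only for a family of five with 40% true effects and 90% power, none of which the SAP states. In larger families with few true effects BH at 0.2 is the stricter rule (40% against 60% for any false positive with two true of twenty). The undefined family is a gap that analysts can fill sensibly by naming the tests when the BH results are tabulated. Because the unadjusted p-values are printed as well, a reader will see any outcome with p > 0.05 for what it is. Only secondary outcomes are touched.
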